5. INTRODUCTION

5.1. Background

ACE-083 is a recombinant fusion protein consisting of a modified form of human follistatin (FST) linked to a human IgG2 Fc domain. Follistatin is a member of the transforming growth factor (TGF)- β superfamily, a large family of structurally related cytokine-like proteins and cell surface receptors that play pivotal roles in the development, differentiation, and maturation of virtually all cells and tissues.¹ Follistatin has been shown to be a potent activin antagonist through its role as a natural ligand trap, functioning as a key regulator of activin activity in body tissues.² Growth and differentiation factor 8 (GDF8), also known as myostatin, is a powerful negative regulator of skeletal muscle development and growth.³ Inhibition of the modulating effects of both activin and myostatin on skeletal muscle growth has been identified as a promising therapeutic approach for degenerative diseases of skeletal muscle.⁴ Unlike myostatin, in which the expression and site of action is primarily restricted to skeletal muscle, activin is produced in many different tissues and mediates a wide range of biologic processes in animals and humans, throughout all stages of development.⁵ The challenge for therapeutic intervention in muscle diseases, therefore, has been in the selective inhibition of activin/myostatin activity only in the target tissue (i.e., skeletal muscle) in order to prevent or minimize undesirable off-target effects due to broad systemic inhibition of activin. ACE-083 has been engineered and developed as a locally-active ligand trap of activin and myostatin in addition to other ligands. The properties of ACE-083 are such that the drug remains primarily within the muscle(s) injected to increase mass and strength of the particular muscle(s).

As described in the ACE-083 Investigator's Brochure (IB), a number of nonclinical pharmacology studies have been conducted with ACE-083 to define the ligand-binding properties of the molecule and assess its anabolic effects on skeletal muscle in normal animals and in a mouse model of muscle disease. Preclinical studies in normal mice and rats have demonstrated increased muscle mass as a result of increased fiber hypertrophy and not hyperplasia. This ACE-083-induced muscle hypertrophy has also been shown to translate to functional improvement in muscle strength in normal mice. ACE-083 has also been evaluated in a well-established mouse model of human Duchenne muscular dystrophy as representative of a degenerative muscle disorder. ACE-083 treatment in these mice resulted in significant increases in the mass of the injected muscle. These studies provide evidence that local inhibition of activin/myostatin by ACE-083 can increase muscle mass even in animals with a degenerative skeletal muscle disease.

In addition, Study A083-01, a phase 1, double-blind, placebo-controlled, dose-ranging study designed to evaluate the safety, tolerability, pharmacokinetics, and pharmacodynamics of local muscle injections of ACE-083 in healthy postmenopausal women has been completed.

Forty-two subjects have received ACE-083 at dose levels of 50 mg to 200 mg administered as single or multiple injections into either the right rectus femoris or right tibialis anterior muscle. ACE-083 was generally safe and well tolerated in this study with no serious adverse events or grade ≥ 3 events reported. A significant dose-dependent change in volume of the injected muscle was seen in the treated versus placebo group.

5.2. Study Rationale

The initial proposed indication for ACE-083 is facioscapulohumeral muscular dystrophy (FSHD), which is the third most common muscular dystrophy and has an autosomal dominant pattern of inheritance in most patients compared to a less common sporadic form which affects approximately 10-30% of patients.^{6,7} FSHD has a prevalence of 1:15,000-1:20,000.^{6,7} FSHD is characterized by complex genetic mechanisms relating to the double homeobox protein 4 gene (DUX4). DUX4 is normally repressed through epigenetic mechanisms in somatic cells and is derepressed in FSHD leading to toxic damage to skeletal muscle cells. The DUX4 gene is located in the D4Z4 microsatellite array in the 4q35 region. In FSHD1, one D4Z4 allele is contracted (1 to 10 repeat units) and has been associated with DNA hypomethylation and chromatin structural changes. FSHD2 accounts for about 5% of FSHD cases and has been characterized by hypomethylation of both normal D4Z4 alleles. Mutations in the SMCHD1 gene resulting in changes in the D4Z4 chromatin structure have been linked to FSHD2. Both types are phenotypically indistinguishable.⁸ Other rare atypical variants of the disease can also manifest in the setting of a genetic diagnosis.

FSHD patients typically present in their second decade of life and live a normal lifespan. The disease is clinically characterized by slowly progressive focal asymmetric areas of muscle weakness involving the facial, scapular, upper arm, lower leg, and abdominal muscles. Biceps and triceps involvement can affect upper arm flexion and extension limiting ability to lift objects and perform activities of daily living. Weakness of the tibialis anterior (TA), a commonly affected lower extremity muscle in FSHD patients, often results in impaired dorsiflexion and foot drop. Foot drop can lead to gait instability and falls requiring the use of braces, walking devices, and wheelchairs. About 20% of FSHD patients become non-ambulatory. Other clinical complications associated with FSHD may involve respiratory muscle weakness, resulting in pulmonary complications, retinovascular disease, chronic pain, and hearing loss.⁹ Laboratory and muscle biopsy findings are often non-specific and therefore are not required for diagnosis. Elevations in creatine kinase (CK) can be seen but are often normal in asymptomatic patients. Muscle biopsy can show variable changes in muscle fiber size (both hypertrophy and atrophy) and inflammatory cellular infiltrates.¹⁰

The management of the disease is based on supportive care including pain management, physical therapy, walking devices or braces, and surgical procedures including those to stabilize the scapula and improve shoulder function. There is an extremely high unmet need for drug development in FSHD as there is no approved disease-modifying therapy for this unrelenting disease. Clinical trials have evaluated multiple systemic treatments including prednisone, albuterol, strength training, and a myostatin inhibitor without definitive positive results.⁸ Given the frequent involvement of isolated muscles such as the TA and biceps brachii (BB), the localized action of ACE-083 could provide meaningful improvements in a patient's muscle strength, function, and quality of life.

6. OBJECTIVES AND ENDPOINTS

Table 3: Objectives and Endpoints

Part 1

Objectives	Endpoints
Primary	

 • To evaluate the safety and tolerability of ACE-083 in patients with FSHD 	
 • Presence and nature of AEs including injection site reactions and changes in clinical laboratory parameters.
Secondary	

 • To determine the recommended dose level(s) of ACE-083 for Part 2 • To evaluate changes in muscle volume and intramuscular fat fraction of the injected muscle • To evaluate changes in strength of the injected muscle • To estimate the systemic exposure of ACE-083 when administered as a local muscle injection 	
 • Recommendation from SRT • Percent change from baseline in total muscle volume of the injected muscle • Percent and absolute change from baseline in intramuscular fat fraction of the injected muscle • Percent change from baseline in strength measurements • Systemic exposure by changes in serum concentrations over time
Exploratory	

 • To evaluate changes in motor function related to the injected muscle • To evaluate changes in patient-reported measures of FSHD-HI total score and subscale scores 	
 • Percent change from baseline in functional assessments • Percent change from baseline in FSHD-HI total score • Percent change from baseline in FSHD-HI subscale scores

Part 2

Objectives	Endpoints
Primary	

 To determine whether treatment with ACE-083 increases total muscle volume of the injected muscle in patients with FSHD 	
 Percent change from baseline in total muscle volume of the injected muscle
Secondary	

 To determine whether treatment with ACE-083 decreases intramuscular fat fraction of the injected muscle To determine whether treatment with ACE-083 increases strength of the injected muscle To determine whether treatment with ACE-083 improves motor function related to the injected muscle To determine whether treatment with ACE-083 improves patient-reported measures of FSHD-HI total score and subscale scores To evaluate safety and tolerability of ACE-083 To estimate the systemic exposure of ACE-083 when administered as a local muscle injection 	
 Percent and absolute change from baseline in intramuscular fat fraction of the injected muscle Percent change from baseline in strength measurements Percent change from baseline in functional assessments (e.g., six minute walk test distance [tibialis anterior groups], performance of upper limb [PUL] mid-level/elbow dimension assessment [biceps brachii groups]) Percent and absolute change from baseline in FSHD-HI total score as well as percent and absolute change in FSHD-HI subscale scores Presence and nature of AEs including injection site reactions and changes in clinical laboratory parameters Systemic exposure by changes in serum concentrations over time
Exploratory (Part 2, open-label)	

 To assess the effect of treatment with ACE-083 on selected motor function tests 	
 Percent change from baseline in 100-meter timed test (tibialis anterior groups) and PUL high-level/shoulder dimension assessment (biceps brachii groups)

7. STUDY DESIGN

7.1. Overview of Study Design

Study A083-02 is a multicenter, Phase 2 study to evaluate the safety, tolerability, pharmacodynamics (PD), efficacy, and pharmacokinetics (PK) of ACE-083 in patients with FSHD to be conducted in two parts. Part 1 is open-label, dose-escalation (3 months) and Part 2 is randomized, double-blind, placebo-controlled (6 months) with an open-label extension (6 months). Patients who have signed the informed consent form (ICF) and meet the eligibility criteria will be enrolled into the study. Up to 36 patients will be enrolled in Part 1 and up to 56 patients (14 active, 14 placebo per muscle) will be enrolled in Part 2, for a total of up to approximately 92 patients.

Study duration for a patient in Part 1 of the study will be approximately 6 months, including a 1-month screening period, a 3-month treatment period, and a 2-month follow-up period after the last dose. Study duration for a patient in Part 2 of the study will be approximately 15 months, including a 1-month screening period, a 12-month treatment period (6-month double-blind, placebo-controlled and a 6-month open-label extension), and a 2-month follow-up period after the last dose.

If a patient has a positive anti-drug antibody (ADA) result at the last visit, the patient will be asked to return for additional ADA testing approximately every three months, until a negative result is obtained or the result is considered to be stabilized.

Part 1 (dose escalation, open-label)

Part 1 will consist of up to 6 cohorts of patients and will evaluate multiple ascending dose levels of ACE-083 in either the tibialis anterior (TA) or biceps brachii (BB) muscle. Patients in each cohort will be enrolled in a 1-month screening period before beginning treatment.

Cohorts 1a and 1b will be treated in parallel. The dose level that will be administered in Cohort 1a will be 150 mg (3 mL) administered by multiple injections unilaterally into the TA muscle, once every 3 weeks for up to 5 doses. Patients in Cohort 1b will be similarly treated in the BB muscle. The estimated tissue exposure of ACE-083 (mg/g muscle) is expected to be similar for the TA and the BB, as the two muscles are relatively similar in size.

For Cohorts 2a and 2b, the decision to enroll patients and the dose levels that will be administered will be based upon Safety Review Team (SRT) review of safety and, if necessary, imaging data collected in prior cohorts. The planned dose level for Cohorts 2a and 2b is 200 mg, with a maximum possible dose level of 250 mg, to be selected following SRT review of data from prior cohorts.

For Cohorts 3a and 3b, the decision to enroll patients, dose level (maximum 250 mg), muscle tested (TA and/or BB), and unilateral or bilateral dosing will be based upon SRT review of safety and imaging data collected in prior cohorts.

The SRT will meet to review data for each cohort when at least 4 patients within a cohort have completed their Day 43 visit (SRT meetings for a and b cohorts can occur separately or together, depending on recruitment). The SRT may recommend one or more of the following: treatment of the remaining patients at the current dose level; escalation to a higher dose level for the next

cohort; an intermediate (lower) dose level or no treatment of additional patients or cohorts. Recommendations made by the SRT may be relevant to both the TA and BB or specific to one or the other muscle, as safety findings and dose escalation may be specific to each muscle.

Part 2 (randomized, double-blind, placebo-controlled, with open-label extension)

Prior to the initiation of Part 2, a review of safety and efficacy data from Part 1 will be conducted to determine whether cohorts for one or both muscles will be pursued in Part 2, as well as the recommended dose level for each muscle. A total of up to 56 new patients (28 patients per muscle) may be enrolled and randomized (1:1) to receive either ACE-083 (n=14/muscle) or placebo (n=14/muscle) bilaterally to either the TA or BB muscles (but not both). Patients will receive study drug once every three weeks for approximately 6 months (9 doses).

Patients who complete the double-blind treatment period will immediately roll over to open-label treatment of ACE-083, receiving the same dose of active drug, bilaterally in either the TA or BB muscle, once every three weeks for approximately 6 months (8 doses). In Part 2, the SRT will periodically review blinded safety data for each muscle treated.

7.2. Justification for Dose Level

ACE-083 was administered into either the rectus femoris (RF) or TA muscle of healthy post-menopausal women in the Phase 1 Study A083-01 at absolute dose levels per muscle of up to 200 mg (RF) or 150 mg (TA) as either a single dose or repeated dose every 3 weeks. An estimated ACE-083 exposure (mg/g muscle) within the muscle was calculated for each patient using the dose administered to each patient and the size of each patient's RF as measured at baseline by MRI. Exposures of approximately 1.2 to 1.6 mg drug/g muscle every 3 weeks for 2 doses in the RF resulted in the desired effect of an approximately 15% increase in muscle volume. These exposures were considered safe and generally well tolerated following review of safety information.

Considering the overall similarity in size for the TA and BB muscles, as well as the potential for muscle atrophy and fibro-fatty infiltration in FSHD patients, a starting dose level of 150 mg for both the TA and BB is considered appropriate and safe based on the Phase 1 clinical trial results. This starting dose level will protect patient safety and also ensure that the initial exposures achieved within the muscle have the potential to impact efficacy endpoints. All subsequent dose levels (higher or lower) will be determined/confirmed following review of study data and recommendations from the SRT. A maximum absolute dose/muscle of 250 mg following dose escalation has been chosen based on administration feasibility and volume constraints.

7.3. Benefit/Risk Assessment

More information about the known and expected benefits, risks, SAEs, and reasonably anticipated AEs of ACE-083 is provided in the IB.

8. STUDY POPULATION

8.1. Inclusion Criteria

Patients are eligible to be included in the study only if they meet all of the following criteria at screening:

Inclusion Criteria:

1. Age \geq 18 years
2. Genetically-confirmed FSHD1 or FSHD2 (or a first-degree relative with genetically confirmed FSHD1 or FSHD2) and clinical findings meeting FSHD criteria
3. Part 1 TA cohorts:
 - a. 6-minute walk distance \geq 150 meters (without a brace)
 - b. Left and/or right ankle dorsiflexion Medical Research Council (MRC) manual muscle testing (MMT) grade 3 to 4+, inclusive ([Appendix 3](#))

Note: Contralateral side may be MRC MMT grade 3 to 5

Part 1 BB cohorts:

- a. Left and/or right elbow flexion MRC MMT grade 3 to 4+, inclusive ([Appendix 3](#))

Note: Contralateral side may be any MRC MMT grade

Part 2 TA cohorts:

- a. 6MWD \geq 150 and \leq 500 meters (without a brace); a maximum of 20% of enrolled patients with 6MWD \geq 450 meters will be included
- b. Left and right ankle dorsiflexion MRCMMT grade 3 to 4+, inclusive ([Appendix 3](#))

Part 2 BB cohorts:

- a. Left and right elbow flexion MRC MMT grade 3 to 4+, inclusive ([Appendix 3](#))
4. Females of childbearing potential (defined as sexually mature women who have not undergone hysterectomy or bilateral oophorectomy, or are not naturally postmenopausal \geq 24 consecutive months) must have negative urine pregnancy test prior to enrollment and use highly effective birth control methods (abstinence, oral contraceptives, barrier method with spermicide, or surgical sterilization) during study participation and for 8 weeks following the last dose of ACE-083. Hormonal birth control use must be stable for at least 14 days prior to Day 1. Males must agree to use a condom during any sexual contact with females of childbearing potential while participating in the study and for 8 weeks following the last dose of ACE-083, even if he has undergone a successful vasectomy. Patients must be counseled concerning measures to be used to prevent pregnancy prior to the first dose of ACE-083.

5. Ability to adhere to the study visit schedule/procedures, and to understand and comply with protocol requirements
6. Signed written informed consent

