10. TREATMENT OF PATIENTS

10.1. Treatments Administered

Using electromyography (EMG) or ultrasound guidance, each dose of study drug will be administered into the non-tendinous portion of the TA or BB as a series of up to 5 equal-volume injections. The use of EMG or ultrasound guidance will ensure that viable muscle is present at the injection site. If the degree of atrophy or fibro-fatty infiltration poses administration challenges, injections of ACE-083 should be distributed at least 2 cm apart into viable muscle. Injection site locations as well as measures to avoid adjacent nerves and blood vessels and prevent intravascular injection are outlined in the Investigational Product (IP) Handling Guide.

For unilateral dosing, if disease involvement in the lower leg or upper arm is asymmetric, the side that is weakest should be injected provided the MRC criterion is met. For bilateral dosing in Part 1, if only one side is weak (i.e., contralateral side is MRC grade 5), it is acceptable to enroll the patient and to inject only the weak side. If a patient meets inclusion criteria for both the TA and BB, the investigator will choose one target muscle based on the patient's clinical presentation as well as on cohort availability and ability to complete assessments for muscle volume (MRI), strength, and function.

In Part 1, Cohorts 1 and 2, each dose will be administered unilaterally into the same targeted muscle, once every 3 weeks for up to 5 doses. For optional Cohort 3, bilateral dosing may be explored (determined by SRT), with a maximum absolute dose level of 250 mg/muscle administered bilaterally, every 3 weeks for 5 doses.

For Part 2, ACE-083 or placebo (normal saline) will be administered every 3 weeks for approximately 6 months (9 doses). Patients who complete the double-blind treatment period will immediately roll over to open-label treatment of ACE-083, receiving the same dose of active drug, bilaterally in either the TA or BB muscle, once every three weeks for approximately 6 months (8 doses).

The planned dose scheme for Part 1 and 2 is shown below.

Table 4: Cohort Schedule for Study A083-02**Part 1: N= Up to 36 (3-month, dose-escalation, non-randomized, open-label)**

Cohort	Muscle	Dose Level ^a	ACE-083 n
1a	Tibialis anterior	150 mg	6
2a	Tibialis anterior	200 mg ^b	6
3a (optional)	Tibialis anterior	TBD ^b	6

Cohort	Muscle	Dose Level ^a	ACE-083 n
1b	Biceps brachii	150 mg	6
2b	Biceps brachii	200 mg ^b	6
3b (optional)	Biceps brachii	TBD ^b	6

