APPENDIX 2. CLINICAL SAFETY LABORATORY ASSESSMENTS

Table 7: Clinical Safety Laboratory Assessments

Type of Assessment	Details
Hematology	Hemoglobin, hematocrit, platelet count, red blood cell count, white blood cell (WBC) count, and WBC differential
Chemistry	AST, ALT, lactate dehydrogenase (LDH) and isoenzymes 1-5, gamma-glutamyl transpeptidase (GGT), blood urea nitrogen (BUN), creatinine, creatine kinase (CK), myoglobin, aldolase, sodium, potassium, glucose, albumin, total bilirubin
Urine	Urinalysis by dipstick analysis (pH, specific gravity, protein, myoglobin, glucose, ketones, blood, leukocyte esterase, and nitrite)

APPENDIX 3. MEDICAL RESEARCH COUNCIL MANUAL MUSCLE TESTING GRADING SCALE**Grading Scale for Manual Muscle Testing (MMT)¹¹**

MMT Grade	Description
5	Normal strength
5-	Uncertain muscle weakness
4+	Inability to resist against maximal pressure throughout range of motion
4	Ability to resist against moderate pressure throughout range of motion
4-	Ability to resists against minimal pressure throughout range of motion
3+	Ability to move through full range of motion against gravity and to resist against minimal pressure through partial range of motion, then contraction breaks abruptly
3	Ability to move through full range of motion against gravity
3-	Ability to move through greater than one half range of motion against gravity
2+	Ability to move through less than one half range of motion against gravity
2	Ability to move through full range of motion with gravity eliminated
2-	Ability to move in any arc of motion with gravity eliminated
1	A flicker of movement is seen or felt in the muscle
0	No contraction palpable

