#### 4.7.1.2. Muscle Strength

Muscle strength variables consist of the following:

- For cohorts where treatment is administered unilaterally
  - Ankle dorsiflexion (maximum voluntary isometric contraction [MVIC]) for the treated TA muscle [TA cohorts]
    - a. MVIC = maximum force (from 3 measurements) from the hand-held dynamometer.
    - b. The treated TA muscle can be either the right or left side. The treated and untreated sides will remain the same for the individual patient throughout the study.
  - Elbow flexion (MVIC) for the treated BB muscle [BB cohorts]
    - a. MVIC = maximum force (from 3 measurements) from the hand-held dynamometer.
    - b. The treated BB muscle can be either the left or right side. The treated and untreated sides will remain the same for the individual patient throughout the study.
- For cohorts where treatment is administered bilaterally
  - Maximum (of 3 measurements) right ankle dorsiflexion (MVIC) [TA cohorts]
  - Maximum (of 3 measurements) left ankle dorsiflexion (MVIC) [TA cohorts]
  - Maximum (of 3 measurements) right elbow flexion (MVIC) [BB cohorts]
  - Maximum (of 3 measurements) left elbow flexion (MVIC) [BB cohorts]

For each of the MRI and muscle strength variables listed above, the absolute and percent change from baseline will be determined for each side (“Treated”, “Untreated”, and “Treated – Untreated” sides for unilateral dose cohorts; “Left”, and “Right” sides for bilateral dose cohorts) and time. In addition, for bilateral dose cohorts, the average of the absolute change from baseline as well as the average of the percent change from baseline for the left and right sides will also be determined.

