##### MRI and Muscle Strength Variables

###### Unilateral Cohorts

Individual MRI and strength data will be listed.

For each MRI and strength variable, the raw data as well as the absolute and percent change from baseline in the treated TA or BB muscle, untreated TA or BB muscle, and the treated minus untreated TA or BB muscle will be summarized for each scheduled time point.

Least square mean estimates of the effect of ACE-083 and corresponding 90% and 95% confidence intervals will be produced using an analysis of covariance (ANCOVA) for the following variables: TMV percent change from baseline 3 weeks post last dose, CCMV percent change from baseline 3 weeks post last dose, FF absolute change from baseline 3 weeks post last dose, percent change in elbow flexion MVIC 3 weeks post last dose (BB cohorts), and percent change in ankle dorsiflexion MVIC 3 weeks post last dose (TA cohorts).

The ANCOVA model will contain the following covariates:

- COHORT represents the dose level of ACE-083 administered to the muscle.
- BASELINE represents the baseline value of the parameter of interest
- BASELINE\*COHORT represents the interaction of the baseline and cohort

The analysis described above will be performed for the treated side as well as for the difference in treated and untreated sides and will be done separately for the TA and BB cohorts.

For BB patients, the above analyses will be repeated using the patient's "preferred" side used for the PUL test for patients.

Additional analyses may be performed as appropriate.

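### The Part 1 biceps strength contrast divides by the uninjected arm's baseline force, which eligibility allows to be zero or close to it, and the SAP has no rule for that case

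*Protocol*

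**What the plan says.** Protocol 8.1, inclusion criterion 3, requires at least one arm of grade 3 to 4+ in the Part 1 BB cohorts and then adds: "Note: Contralateral side may be any MRC MMT grade". The matching note for the Part 1 tibialis anterior (TA) cohorts sets a floor: "Note: Contralateral side may be MRC MMT grade 3 to 5". Part 2 requires grade 3 to 4+ on both sides for either muscle. The grading scale in Protocol Appendix 3 runs down to grade 0, defined as "No contraction palpable".

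For unilateral dosing with asymmetric disease, Protocol 10.1 says "the side that is weakest should be injected provided the MRC criterion is met". All three BB cohorts in SAP Table 1 are unilateral, with six patients each.

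SAP 4.7.1.2 defines strength as "MVIC = maximum force (from 3 measurements) from the hand-held dynamometer" and says that "the absolute and percent change from baseline will be determined for each side", where the sides are treated, untreated and treated minus untreated. For the unilateral cohorts, SAP 4.7.2.1 names the percent change in elbow flexion MVIC three weeks after the last dose as an ANCOVA variable, with 90% and 95% confidence intervals, and adds: "The analysis described above will be performed for the treated side as well as for the difference in treated and untreated sides".

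**The concern.** A percent change needs a baseline well away from zero. The BB eligibility rule gives no such assurance for the uninjected arm, and the injection rule steers the weakest arms into that position: when one arm is below grade 3, the other must be the injected one. The difference model can therefore meet a denominator of zero, or one so small that ordinary measurement error becomes a very large percentage. Change in strength of the injected muscle is a Part 1 secondary objective. In a cohort of six, one such value can decide the estimate and the width of its interval.

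**Working it through.** The documents give no sample size, power or effect size for Part 1, so there is no planned figure to reproduce.

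**Step 1: can the case arise?** Part 1 BB eligibility needs one arm at grade 3 to 4+ and leaves the other free. An arm at grade 0 to 3- fails the criterion that Protocol 10.1 attaches to injecting the weaker side. It is therefore the untreated side in any of the 18 planned BB patients to whom this applies.

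**Step 2: does the plan protect the denominator?** I found nothing that does.
- Baseline strength is the mean of up to three pre-dose visits (SAP 4.1.4). That steadies it but does not lift it off zero.
- SAP 4.7.2.1 makes no imputations in Part 1 unless otherwise specified.
- The convention in SAP 4.1.5 of replacing a below-limit value by half the limit serves descriptive statistics and does not cover a recorded zero.
- No force floor or minimum untreated grade is given.

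**Step 3: size in a raw mean.** I read the difference as the treated percent change minus the untreated percent change. Let B be one patient's untreated baseline and e the change in that arm. Then:
- untreated percent change = 100 × e / B
- shift in the mean of six = 100 × e / (6 × B)

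The documents give no MVIC values by grade, so the forces are assumptions. With e = 0.5 kg:

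| B (kg) | Untreated change | Shift in mean of six | Mean if the true difference is +10 points in all six |
|---|---|---|---|
| 10 | 5% | 0.8 | 9.2 |
| 5 | 10% | 1.7 | 8.3 |
| 2 | 25% | 4.2 | 5.8 |
| 1 | 50% | 8.3 | 1.7 |
| 0.5 | 100% | 16.7 | -6.7 |
| 0 | undefined | patient leaves the model | not applicable |

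**Step 4: spread.** A simulation of 200,000 cohorts of six assumed other baselines of 10 kg, a true treated gain of 10%, no true untreated change, and an error SD of 0.5 kg per visit. The 5th to 95th percentiles of the raw cohort mean difference were 4.4 to 15.6 with all untreated arms at 10 kg, and -13.9 to 24.6 with one arm at 1 kg. In the second case that one patient supplied a median 84% of the cohort's squared deviation, against 9% when the arm was at 10 kg.

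**Step 5: the planned estimator.** The SAP reports a least-squares mean from a model with baseline, cohort and their interaction, not a raw mean. It does not say which baseline enters the difference model. If it is the untreated arm's, the weak-arm patient is a high-leverage point and part of the shift goes into the slope. With 18 patients, other baselines of mean 10 kg and SD 2 to 4 kg, and least-squares means taken at the overall mean baseline (all assumptions), the median shift is about 4 to 5.5 points at 1 kg and about 7.5 to 11 at 0.5 kg. That is roughly half to two-thirds of the raw-mean shift, with wide ranges.

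**Step 6: absolute scale.** The same 0.5 kg change moves the mean of six by 0.5 / 6 = 0.08 kg, whatever B is.

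**The case against.** A reader might infer that the untreated arm is the control for Part 1 strength. The documents do not support that. Protocol 14.2.3.1 names the screening-to-baseline percent change as the strength control, although the SAP does not carry it forward. SAP 4.7.2.1 also analyses the treated side alone, which does not depend on the other arm.

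A reader might infer that a patient with a zero baseline disappears unseen. That does not follow either. Individual strength data are listed, descriptive statistics carry N, and absolute treated-minus-untreated change is already summarised at each scheduled time.

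A reader might also infer that this could mislead the choice of dose or muscle for Part 2. Protocol 7.1 ties dose decisions between cohorts to safety and imaging data. Part 1 efficacy is reviewed before Part 2, but nothing links that review to this contrast.

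Protocol exclusion 2 lets the investigator exclude patients whose impairment would limit strength testing. It makes grade 0 or 1 arms less likely, but it sets no grade and so does not close the gap. Finally, not every arm below grade 3 is unusable: at grades 2 to 3- a small positive force is plausible, and the problem there is influence, not an undefined value.

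These points narrow the scope and lower the weight. None supplies the missing rule for the difference model.

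**Conclusion.** The point holds for one analysis: the Part 1 BB ANCOVA on the treated-minus-untreated percent change in elbow flexion MVIC. Followed as written, it can lose a patient through an undefined value or return an estimate driven by one patient. The raw-mean shifts of about 8 and 17 points, at baselines of 1 and 0.5 kg, rest on assumed forces and a 0.5 kg change, and the shift in the least-squares mean may be smaller. An undefined value requires a mean baseline of exactly zero, which is most plausible at grade 0 or 1. How many such patients were enrolled, if any, cannot be told from the documents. Severity is minor, because this is a Part 1 secondary estimate and Part 2 requires grade 3 to 4+ on both sides.

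**What to change.** In SAP 4.7.2.1, for the BB cohorts:

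1. Fit the treated-minus-untreated MVIC ANCOVA to the absolute change in all patients. At present that difference is only summarised descriptively.
2. Restrict the percent-change difference ANCOVA to patients whose uninjected arm was grade 3 or above at screening, and report the number excluded by cohort.
3. Keep the treated-side analysis in everyone.
4. State which baseline enters the difference model, and confirm that the difference is one percent change minus the other.

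The restriction uses a grade recorded before treatment, so it cannot depend on outcome. Grade 3 is the floor already set for TA; no force data in the documents support it as an exact threshold. The cost is SAP wording, since screening grades and absolute changes are already collected. The percent-change contrast may lose some patients, number unknown. The absolute contrast gives more weight to stronger arms, so the two should be read together. Eligibility and dosing do not change.
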